### 5.7 Efficacy variables

For the endpoints defined below, further details concerning the derivation of the corresponding analysis variables can be found in Section 11.

#### 5.7.1 Primary efficacy variable

Not applicable.

### 5.7.2 Secondary efficacy variables

Not applicable.

### 5.7.3 Other efficacy variables

All efficacy variables evaluated in this study are considered exploratory.

#### 5.7.3.1 *Exploratory disease activity variables*

- Modified Systemic Lupus Erythematosus Activity Index-2000 (SLEDAI-2K)

The following endpoints are defined:

- Absolute values, absolute change and percent change in modified total SLEDAI-2K score from baseline to each post-baseline analysis visit (including EOT);
- Absolute values, absolute change and percent change in SLEDAI-2K mucocutaneous subscore, musculoskeletal subscore, and combined mucocutaneous and musculoskeletal subscores from baseline to each post-baseline analysis visit (including EOT).

In addition, for the modified total SLEDAI-2K score, the following endpoints are defined:

- Occurrence of an increase from baseline of > 3.

In addition, for subjects presenting with arthritis, the following endpoint is defined:

- Number of affected joints at baseline;
- Number of affected joints and change from baseline to each post-baseline analysis visit.

- Physician's Global Assessment of disease (PGA)

The following endpoints are defined:

- Absolute value, absolute change and percent change in PGA score from baseline to each post-baseline analysis visit (including EOT).

#### 5.7.3.2 *Exploratory biomarker variables*

- ANA, anti-dsDNA, complement factors and exploratory biomarkers

The following parameters are assayed by the central laboratory:

- ANA, anti-dsDNA, complement C3 and C4 (all visits except Visit 3);
- IgM, IgG, IgA, CRP, fibrinogen, and B lymphocyte stimulator (BLyS) (Visit 2 and Visits 4 to 7).

The following parameter is assayed by Translational Science Biology:

- C-X-C motif chemokine ligand 10 (CXCL10) (EDTA-plasma; Visit 2 and Visits 4 to 7).

The following endpoints are defined:

- Change in immunoglobulin serum levels (IgG, IgM, IgA) from baseline to each post-baseline analysis visit;
- Change in ANA and anti-dsDNA antibody titers from baseline to each post-baseline analysis visit;
- Change in serum complement components C3 and C4, CRP, fibrinogen, BLyS and CXCL10 from baseline to each post-baseline analysis visit.

If the number of values recorded as below or above the limit of quantification is more than one third overall, the parameter is only described as a categorical variable (value at each analysis visit).

Categories are defined using the reference ranges and the reportable ranges provided by the central laboratory.

**Table 5** Exploratory biomarker variables evaluated during the study

| Parameter (unit)          | Reference Ranges | Reportable Ranges | Categorization   |
|---------------------------|------------------|-------------------|--|
| ANA titer                 | < 40             | <40; >=640        | < 40, 40, 80, 160, 320, >=640                            |
| anti-dsDNA (U/mL)         | < 100            | 50; 1000          | < 1.0, 1.0 - 99.9, >= 100                                |
| Complement C3 (g/L)       | 0.9 ; 1.8        | 0.50; 1125.00     | < 0.90, 0.90 - 1.80, > 1.80                              |
| Complement C4 (g/L)       | 0.18 ; 0.45      | 0.40; 700.00      | < 0.05, 0.05 - 0.17, 0.18 - 0.45, > 0.45                 |
| C Reactive Protein (mg/L) | < 8.00           | 4.00; 999.00      | < 4.00, 4.00 - 7.99 , >= 8.00                            |
| Fibrinogen (g/L)          | 2.1 ; 4.7        | 0.01; 7.0         | < 0.5, 0.5 - 1.0, 1.1 - 2.0, 2.1 - 4.7, 4.8 - 5.9, > 5.9 |
| Immunoglobulin A (g/L)    | 0.4 ; 3.5        | 0.15; 54.00       | < 0.4, 0.4 -3.5, > 3.5                                   |
| Immunoglobulin G (g/L)    | 6.5 ; 16         | 0.70; 340.00      | < 6.5, 6.5-16.0, >16.0                                   |
| Immunoglobulin M (g/L)    | 0.5 ; 3          | 0.08; 33.00       | < 0.5, 0.5 - 3.0, > 3.0                                  |
| BAFF/ BLyS (pg/mL)        | 584 ; 1186       | 63; 4000          | 63, 63-583, 584-1186, 1187-4000, >4000                   |
| CXCL10 (ng/L) *           | NA               | NA                | NA   |

\* assayed by Translational Science Biology at Actelion

For parameters considered as continuous variables, the change is evaluated in terms of absolute change and percent change from baseline to each post-baseline analysis visit.

- Blood lymphocyte subsets

Blood samples for lymphocyte subset analysis are taken at Visit 2 (Randomization/ Day 1), Visit 6 (EOT) and Visit 7 (EOS) and assayed by Translational Science Biology at Actelion.

The following endpoints are defined:

- Change in blood lymphocyte subsets from baseline to EOT and EOS.

The complete list of parameters and units is provided in Section 11.

## 5.8 Safety variables

More details of the computation of safety variables can be found in Section 11.

### 5.8.1 Adverse events

All adverse events (AEs) occurring during the study period (from informed consent signature up to the EOS visit) are recorded on the eCRF. The original verbatim terms used by investigators to identify AEs are mapped to preferred terms (PT) using the most current version of the MedDRA dictionary at the time of database closure.

#### 5.8.1.1 *Treatment-emergent adverse events*

A treatment-emergent adverse event (TEAE) is any AE temporally associated with the use of study treatment (from study treatment initiation until Visit 7 [EOS]) irrespective whether considered by the investigator to be related to study treatment or not.

An AE is considered a TEAE if the start date is after (>) the first study treatment intake or the start date is on the same day as the first study treatment intake and the answer to 'Did this adverse event start at visit 2 or on first day of re-initiation following study drug intake?' is equal to 'Yes' indicating that the AE started after first intake of study treatment.

#### 5.8.1.2 *Related treatment-emergent adverse events*

An AE is considered related if the investigator ticked 'Yes' to the question 'Relationship to study treatment' or if it is missing.

### 5.8.2 Deaths

#### 5.8.2.1 *All deaths*

Date of death and primary cause are recorded on the 'Death' eCRF page.

#### 5.8.2.2 *Adverse events leading to death*

AEs with an outcome reported as 'death' are considered as AEs leading to death.

### 5.8.3 Serious adverse events

An AE is considered serious if the investigator ticked ‘Yes’ on the question ‘Serious?’ on the Adverse Event eCRF or if it is missing.

#### 5.8.3.1 Fatal serious adverse events

An AE is considered fatal and serious if the investigator ticked ‘Yes’ on the question ‘Serious?’ and if the outcome is equal to ‘Death’ on the Adverse Event eCRF.

### 5.8.4 Adverse events leading to discontinuation of study treatment

These are AEs with ‘Action taken with study drug’ recorded as ‘permanently discontinued’ on the Adverse Event eCRF.

### 5.8.5 Other significant adverse events

#### 5.8.5.1 AE of special interest

An AE is considered to be an AE of special interest (AESI) if it is treatment emergent and belongs to any of the categories listed below (the list of corresponding MedDRA PT is defined in the latest AESI list enclosed in [Appendix 15.2.2](#)):

- Effect on heart rate and rhythm AESI (including hypotension)
- Cardiovascular AESI
- Hypertension AESI
- Liver AESI (Hepatobiliary disorders/ liver enzyme abnormality)
- Pulmonary AESI
- Macular edema AESI
- Infection AESI
- Herpetic infections AESI
- Skin malignancy AESI
- Non-Skin malignancy AESI
- Stroke AESI
- Seizure AESI

#### 5.8.5.2 SLE flares reported as AEs

These are AEs with ‘Does this Adverse Event represent a clinical manifestation of SLE flare?’ ticked ‘Yes’ on the ‘Adverse Event’ eCRF page.

### 5.8.6 Vital signs and body weight

Vital signs include Systolic Blood Pressure (SBP) (mmHg), Diastolic Blood Pressure (DBP) (mmHg) and body weight (kg).

#### 5.8.6.1 Blood pressure

SBP and DBP are collected at all visits. At Visit 1 (Screening), SBP and DBP are measured sequentially, twice in the supine and twice in the standing position. In this case

the mean of the two values by position as recorded in the eCRF is used for the analysis. At Visit 2 (Randomization/ Day 1) and at re-initiation, supine SBP and DBP are measured once pre-dose and then once hourly until 6 hours post-dose. At each post-baseline pre-dose assessment, SBP and DBP are measured twice in the supine position and the mean of the two values as recorded in the eCRF is used for the analysis.

The following endpoints are defined:

- Change from baseline to each post-baseline assessment up to EOS (i.e., each post-dose hourly time point on Day 1 and each post-dose analysis visit up to EOS);
- Occurrence of treatment emergent notable abnormalities in blood pressure.

The following analysis parameters are defined:

- Supine SBP (mmHg)
- Standing SBP (mmHg) (only at Visit 1)
- Supine DBP (mmHg)
- Standing DBP (mmHg) (only at Visit 1)

For supine SBP and DBP, the occurrence of treatment emergent notable abnormalities is assessed according to the criteria defined in the table below:

**Table 6        Notable abnormalities in blood pressure**

| Analysis Parameter | Analysis Criterion                                    |
|--------------------|---|
| Supine SBP (mmHg)  | Value $\leq$ 90 and decrease $\geq$ 20 from baseline  |
|                    | Value $\geq$ 140 and increase $\geq$ 20 from baseline |
|                    | Value $\geq$ 160                                      |
| Supine DBP (mmHg)  | Value $\leq$ 50 and decrease $\geq$ 15 from baseline  |
|                    | Value $\geq$ 90 and increase $\geq$ 15 from baseline  |
|                    | Value $\geq$ 100                                      |

Abnormalities are defined for each post-baseline time point and analysis visit individually. In addition, the occurrence of at least one abnormality for each of the criterion is derived on the subject level on the following time intervals: on Day 1 (from 1 hour post-dose through to discharge), after Day 1 (from discharge through to EOT) and at any post-baseline time point/analysis visit (from 1 hour post-dose through to EOS).

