### ***1.3.2.3 Safety and tolerability***

Single doses of 1 mg, 3 mg, 10 mg, and 25 mg were evaluated in healthy subjects. The 10 mg dose was identified as the maximal tolerated single dose of ACT-334441. In the 25 mg group, a serious life-threatening event of hypotensive shock (preferred term: circulatory collapse) was reported. Per study stopping criteria, dose escalation was halted after the 25 mg dose group. One event of non-serious syncope of moderate intensity was also reported in the 10 mg treatment group.

Multiple doses of 0.5 mg, 1 mg, 2 mg, and 4 mg ACT-334441 were administered o.d. for up to 35 days. All doses were found to be well tolerated, with no serious adverse events (SAEs) and no adverse events (AEs) leading to treatment discontinuation. The most frequently reported AEs in the active treatment groups were headache (37.5%), chest pain (all combined chest pain, chest discomfort, musculoskeletal chest pain, non-cardiac chest pain; 33.3%), followed by nasopharyngitis (16.7%), and dizziness (16.7%).

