##### **Cardiovascular**

4. History or presence of cardiac rhythm disorders (e.g., sinoatrial heart block, second or third degree AV block, symptomatic bradycardia, atrial flutter or atrial fibrillation, ventricular arrhythmias, cardiac arrest).
5. Resting HR  $< 55$  bpm as measured by the pre-dose 12-lead ECG on Day 1; an increased QT corrected for heart rate on the basis of Fridericia's formula (QTcF) interval of  $> 470$  ms (females),  $> 450$  ms (males) at Screening, or on Day 1 ECG prior to study treatment initiation.

6. History or presence of ischemic heart disease.
7. History or presence of myocarditis or endocarditis.
8. Presence of valvular heart disease associated with symptoms or hemodynamic change.
9. History of syncope associated with cardiac disorders.
10. History or presence of cardiac failure.
11. Systemic arterial hypertension not controlled by medication according to investigator judgment.
12. History or presence of vascular thrombosis at any time or a history of pregnancy morbidity in the context of anti-phospholipid antibody syndrome within 5 years prior to Randomization.
13. Clinically relevant hypotension according to investigator's judgment or orthostatic hypotension (i.e., > 20 mmHg decrease in SBP or > 10 mmHg decrease in DBP from supine to standing position measured between 1 and 3 minutes after standing) at Screening.
14. Known pulmonary arterial hypertension of functional class III or IV.

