#### **5.1.10 Management of clinical events and study-specific criteria for interruption / premature discontinuation of study treatment**

##### **5.1.10.1 Cardiovascular**

Subjects must be permanently discontinued from study treatment if any of the following occurs:

- HR < 40 bpm at two consecutive hourly 12-lead ECG post-dose on Day 1 (or on days of re-initiation following study treatment interruptions), or
- SBP < 90 mmHg at two consecutive hourly BP measurements post-dose on Day 1 (or on days of re-initiation following study treatment interruptions), or
- The subject does not meet the criteria for discharge from the hospital on Day 1 (or on days of re-initiation following study treatment interruptions) after 12-hour post-dose monitoring [see [Appendix 4](#)], or

- QTcF > 500 ms is observed at any time throughout the study, as documented by 12-lead ECG.

In addition, the investigator should consider permanent discontinuation of study treatment if a subject reports at any time symptomatic bradycardia or hypotension (e.g., syncope).

Follow-up monitoring will have to be provided until the event resolves, the condition is stable, or the change is regarded as no longer clinically relevant.

Continuous ECG monitoring is recommended for subjects who meet study treatment discontinuation criteria related to bradycardia or other arrhythmia. Subjects who are permanently discontinued should not be discharged from the monitored setting before vital signs return to near baseline values and until there is no persisting ECG abnormality (e.g., QT prolongation, AV block second degree or higher) or ongoing AE requiring (continued) hospitalization, or until medically indicated. Any clinically relevant findings meeting the definition of an AE will be recorded accordingly in the eCRF.

In case of any signs and symptoms of bradycardia or other arrhythmia (e.g., syncope, palpitations, dizziness) at any time during the study treatment, the CSA should be consulted. In case a cardiac origin of any event is suspected, permanent discontinuation of study treatment should be considered.

In case subjects develop new or worsening of pre-existing hypertension during the course of the treatment with the study treatment that in the opinion of the investigator cannot be adequately controlled by medications, study treatment should be permanently discontinued.

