**Table 4 Safety areas of interest**

Safety area of interest [See Section 5.1.10]	Specific study stopping criteria being applied to stop subject / study
Cardiovascular	

• HR < 40 bpm at two consecutive hourly 12-lead ECG post-dose (Day 1 or re-initiation)

• SBP < 90 mmHg at two consecutive hourly BP measurements post-dose (Day 1 or re-initiation)

• Subject not meeting criteria for discharge from the hospital (Day 1 or re-initiation)

• QTcF > 500 ms at any time as documented by 12-lead ECG

• Symptomatic bradycardia or hypotension (e.g., syncope)

Immune system and Infections	

• Confirmed total lymphocyte count < 200 cells/<math>\mu</math>L

• Clinically relevant infection (e.g., serious infection, opportunistic infection)

Respiratory system	

• FEV1 and/or FVC > 15% decrease from the study baseline values which has been confirmed at repeat testing

• Persistent respiratory AEs (e.g., dyspnea)

Liver	

• Abnormal LTs or signs and symptoms suggestive of DILI as explained in the study protocol [Section 5.1.10.5]

Ocular	

• Macular edema confirmed by Ophthalmology Safety Board

AE = adverse event; BP = blood pressure; DILI = drug-induced liver injury; ECG = electrocardiogram; FEV1 = forced expiratory volume in 1 second; FVC = forced vital capacity; HR = heart rate; LT = liver test; SBP = systolic blood pressure.

If the study is suspended or prematurely terminated for any reason, the investigator in agreement with Actelion must promptly inform all enrolled subjects, and ensure their appropriate treatment and follow-up, as described in Section 9.2 for subjects prematurely withdrawn from the study. The investigator may be informed of additional procedures to be followed in order to ensure that adequate consideration is given to the protection of the subjects' interests.

In addition, if the investigator suspends or terminates the study without prior agreement from Actelion, the investigator must promptly inform Actelion and the IRB/IEC, and provide both with a detailed written explanation of the termination or suspension.

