### 11.2.17.1 *Blood pressure*

For Supine SBP / DBP (mmHg):

**Baseline** is defined as the mean (computed in the eCRF) of the 2 measurements performed on Visit Day 1, at pre-dose (Category equal to 'MEAN'). If missing, it is replaced by the last non missing value recorded prior to the first dose.

**Analysis value** is defined as the value at the visit/ time point (numeric result in standard units). For assessments performed on Visit Day 1, after pre-dose, the analysis value at the time point is retrieved from the record available. For all visits performed after Day 1, the analysis value is retrieved from the record populated with VSCAT = 'MEAN'.

Abnormalities, as defined in table 'treatment emergent notable abnormalities' are populated for each post-baseline assessment individually. In addition, the occurrence of at least one 'Low' and at least one 'High' treatment-emergent abnormality is derived on the subject level for the following time intervals: on Day 1 (from 1 hour post-dose up to discharge), after Day 1 (from discharge on Day 1 through Visit 7 (EOS)) and at any time post-baseline.

For Standing SBP / DBP (mmHg), only the **Analysis value** at the visit is populated.

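### SAP Table 6 has a single low-systolic criterion, so a subject stopped under the protocol's SBP < 90 rule from a baseline of about 108 mmHg or lower can be absent from the summary of notable BP abnormalities

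*SAP*

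**What the plan says.** SAP 5.8.6.1, Table 6, defines notable abnormalities in supine blood pressure. For low systolic pressure there is one row: "Value $\leq$ 90 and decrease $\geq$ 20 from baseline". Both conditions must hold at the same time point. High systolic pressure has a combined row and also a stand-alone row at 160 mmHg or above. SAP 10.9.5 summarises these flags by treatment group with 95% Clopper-Pearson intervals.

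Protocol 5.1.10.1 requires permanent discontinuation for "SBP < 90 mmHg at two consecutive hourly BP measurements post-dose on Day 1", and likewise on a re-initiation day. It has no change-from-baseline condition. Protocol Table 4 lists the same criterion among the events that count towards the study stopping rules in Section 9.3.

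Eligibility sets no numeric floor on SBP. Exclusion criterion 13 (Protocol 4.4) refers to "Clinically relevant hypotension according to investigator's judgment or orthostatic hypotension", so low-normal baselines can be enrolled. Protocol Appendix 7 leaves the definition of abnormal BP values to the SAP.

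**The concern.** The reporting rule and the stopping rule use nearly the same threshold, but only the reporting rule also requires a fall of 20 mmHg. In a subject who starts low, pressure can drop below 90 and force discontinuation without meeting the reporting rule. The table a reader would consult for low pressure by dose could then show no case in an arm where a subject was stopped for low pressure.

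Safety and tolerability is a main objective, and hypotension is a named AESI area in Protocol Appendix 3. In the 25 mg single-dose group of Phase 1, "a serious life-threatening event of hypotensive shock (preferred term: circulatory collapse) was reported" and escalation was halted. With 12 subjects per active arm, one subject more or less is visible in the table.

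**Working it through.** The plan states no figure on this point, so there is none to reproduce. The check applies the two rules as written and compares them.

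**Inputs**
- Table 6 flag: v ≤ 90 and b − v ≥ 20, where b is baseline and v is a post-dose reading.
- Stopping criterion: v1 < 90 and v2 < 90 at consecutive hourly readings.
- Baseline: SAP 11.2.17.1 says it "is defined as the mean (computed in the eCRF) of the 2 measurements performed on Visit Day 1, at pre-dose", so half-integers are possible. SAP 5.8.6.1 instead says one pre-dose reading is taken on Day 1. The two should be reconciled, but the choice moves the result below by only 0.5 mmHg.

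**Where the rules part.** A reading below 90 is unflagged if b − v < 20, that is, b < v + 20. Since v < 90, b must be below 110. With whole-number readings, v is at most 89 and an unflagged fall is at most 19, so b is at most 89 + 19 = 108. With a half-integer baseline the largest unflagged fall is 19.5, so b is at most 108.5.

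| Baseline | Two readings | Largest fall | Stopped? | Flagged? |
|---|---|---|---|---|
| 110 | 89, 89 | 21 | yes | yes |
| 109 | 89, 89 | 20 | yes | yes |
| 108 | 89, 89 | 19 | yes | no |
| 105 | 86, 86 | 19 | yes | no |
| 100 | 85, 84 | 16 | yes | no |

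From a baseline of 100, a lowest value anywhere from 81 to 89 is unflagged; from 95, anywhere from 76 to 89. A subject is missed only if no reading on the study meets both Table 6 conditions.

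**Pool in whom this can happen (assumption).** The documents give no baseline SBP distribution. Taking it as normal with mean m and SD s, the share below 110 is Φ((110 − m)/s).
- m = 125, s = 10: Φ(−1.50) = 0.067, or 0.8 of 12
- m = 120, s = 12: Φ(−0.83) = 0.202, or 2.4 of 12
- m = 115, s = 15: Φ(−0.33) = 0.369, or 4.4 of 12

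**Effect of one omission in an arm of 12 (SAP 9.1.1 method).**
- 0/12: 0%, upper limit 1 − 0.025^(1/12) = 26.5%.
- 1/12: 8.3%, lower limit 1 − 0.975^(1/12) = 0.2%; upper limit, the 0.975 quantile of Beta(2, 11), = 38.5%.

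**Comparison within the SAP.** Table 7 has a stand-alone row for heart rate below 40 bpm, the threshold of the protocol's heart-rate stopping criterion, so every subject stopped on that criterion falls in it. Table 6 has no such row for SBP.

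**The case against.** The two documents do not contradict each other. The protocol hands the reporting definition to the SAP, and requiring a fall from baseline is a common way to isolate change on treatment. A stopping rule protects the individual and need not match it. Table 6 is headed as notable BP abnormalities; it is not presented as a hypotension count or a tally of stopping events. Its row is also looser than the stopping rule in two respects: it includes exactly 90, and a single reading is enough. All of this stands.

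A reader might infer that such a case vanishes from the report. The documents do not support that:
- SAP 10.9.5 plans hourly SBP summaries by arm, which under SAP 10.2 include the minimum, as well as boxplots with the abnormality thresholds overlaid and listings of all values.
- SAP 10.3.1.3 and 10.9.2.3 tabulate discontinuations with reasons and AEs leading to discontinuation.
- SAP 10.9.2.4 and 15.2.2 cover hypotension preferred terms among the AESIs, with relative risks against placebo, provided an AE is reported. Protocol 7.2.4 requires that for clinically relevant BP abnormalities.

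What remains is narrower. None of these displays counts, by arm, the subjects with SBP below 90 at two consecutive readings. SAP 5.8.9 defines reasons for non-discharge, but no part of SAP Section 10 analyses them.

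A reader might also infer that the study hold could be undercounted. Protocol 9.3 counts discontinuations directly and does not use Table 6. A separate SAP for the IDMC closed sessions exists (SAP Section 1) and is not available here, so the gap is shown only for the SAP for the clinical study report.

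The Phase 1 event should not be over-read. It followed a single 25 mg dose; Protocol 1.3.2.3 reports no relevant BP change with repeated dosing at 0.5 to 4 mg, the range used in this trial. Protocol 5.1.4.2 names first-dose effects on heart rate and AV conduction, not on blood pressure.

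**Conclusion.** The point holds as a reporting gap of modest weight. A subject who meets the protocol's SBP stopping criterion from a baseline of about 108 mmHg or lower can be absent from the summary of notable BP abnormalities, and no summary described in this SAP counts that criterion by arm. This follows from the two rules as written and needs no assumption.

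The size does rest on assumptions. For mean baseline SBP of 115 to 125 and SD of 10 to 15, about 7% to 37% of subjects start below 110, or roughly 1 to 4 of 12 per arm. It is tempting to read that as the number of missed cases. It is only the pool at risk: a miss also needs two consecutive readings below 90 and no reading that satisfies Table 6, and the documents give no rate for either. Few cases are expected at these doses, so one omission (1/12 shown as 0/12) is the relevant scale. No safety decision during the trial is shown to depend on this row.

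**What to change.** Keep the existing Table 6 row. Add one row to Table 6 and to SAP 10.9.5 for the protocol's existing criterion: SBP below 90 at two consecutive hourly post-dose readings on Day 1 or the re-initiation day, by arm, with the Clopper-Pearson interval already planned there.

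A row for any post-dose SBP below 90 is not recommended as it stands. With no eligibility floor, it would count subjects who were already below 90 before dosing. If such a row is wanted, limit it to subjects whose baseline was not below 90.

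The cost is one subject-level flag from hourly data already collected and one more descriptive row. No clinical threshold changes.
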